10.3.2 Randomization procedure

Randomization will be performed by site in random permuted blocks of 6 by allocation order. A randomization sequence will be produced and integrated into the electronic case report form to define the randomized treatment order (X or Y device) and provide the investigator with this information during the enrolment visit.

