6.2 Hypothesis

The primary hypothesis is that the microprocessor based C-Brace technology will help moderately active patients to improve balance compared to a non-microprocessor controlled KAFO/SCO.

As a consequence, the C-Brace should help reduce the risk of falling/falls in these patients and eventually make them more independent in their daily life activities including their job and improve their quality of life, which represents the secondary hypothesis of the study.

ottobock.	CLINICAL INVESTIGATION PLAN	Document number:	PD-PS00120016A-001
		Version number:	7
Project name	Clinical trial comparing C-Brace to KAFO/SCO	Project no.	PS00120016A

7 Study design

This is a prospective international multicenter randomized controlled cross-over open-labeled trial.

The study will have multiple sites in the United States, Germany, Netherlands and Austria. In total 56 patients will be recruited. Patients can be enrolled in a competitive manner without any allocation.

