7.1 Experimental plan

After obtaining informed consent, patients will be screened. Patients fulfilling inclusion/exclusion criteria will be enrolled in the study. After screening, a first baseline assessment will be conducted. Within maximum 48 hours, a second set of baseline data will be collected. Afterwards the participants will be randomly assigned to be fitted either with C-Brace or maintain his/her KAFO/SCO. The randomization procedure will be concealed and assigned off-site. After fitting, an accommodation period follows that will last up to 14 days prior home use. The first follow-up data collection will occur after 3 months after the initial home use period. Afterwards, the patients will cross over to KAFO/SCO or C-Brace, respectively. The participants who were fitted with C-Brace will cross over to KAFO/SCO and vice versa. Another accommodation phase will be offered for both C-Brace and KAFO/SCO wearers to ensure that the patient can properly use both devices before the cross-over home use period. The second follow-up data collection will occur after 3-months of home use. At the end of the study, the patients can choose to keep C-Brace until reimbursement or return to their original KAFO/SCO.

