7.2 Measures taken to minimize bias

The research center will delegate the role of assessor to one trained employee. The assessor will be responsible for evaluating functionality of participants in the performance-based tests in all phases of the study. During all performance tests, patients will be instructed to refrain from giving any comments. The certified prosthetist (CPO) and physical therapist cannot be blinded.

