9.1 Number of patients to enroll

Up to 150 patients fulfilling the inclusion and exclusion criteria will be enrolled in the study. At least 56 subjects passing screening will be randomized. All sites are allowed to recruit patients competitively according to their possibilities. Patient screening and enrollment will be performed in close collaboration with the sponsor to avoid over-recruitment.

Potential patients will be called by the participating centers and may be pre-screened for study eligibility. In addition, patients contacting the centers or visiting them on a routine basis can be also pre-screened.

Once a potential participant using a unilateral KAFO or SCO has been identified, study clinician may contact the potential patient or study staff will contact the potential patient on behalf of the principal investigator, starting with a letter followed by a phone call to the potential patient.

A screening log will be tracked.

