15.3 Amendments to the Clinical Study Protocol

All amendments to the clinical study protocol should be agreed between the Sponsor and the Investigator and be recorded with a justification for the amendment. The Investigator or the Sponsor will not implement any deviation from, or changes of, the clinical study protocol without mutual agreement and review/approval from the EC, and other agencies as required, of a proposed amendment. The only exceptions are where necessary to eliminate an immediate safety hazard to study patients,

ottobock.	CLINICAL INVESTIGATION PLAN	Document number:	PD-PS00120016A-001
		Version number:	7
Project name	Clinical trial comparing C-Brace to KAFO/SCO	Project no.	PS00120016A

or when the changes involve only administrative aspects of the clinical study (e.g. change in monitor(s), change of telephone number(s)).

The party initiating an amendment must confirm it clearly in writing and it must be signed and dated by the Sponsor, the Coordinating Investigator and the Principal Investigators. Clinical study protocol amendments will be submitted to the appropriate ECs and competent authorities in line with pertinent national regulatory requirements.

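### A single fixed block of 6 within each site, printed in the protocol that open-label sites hold, weakens allocation concealment: about one in six device orders can be known in advance

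*Combined protocol and SAP*

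**What the plan says.** Section 10.3.2 (Randomization procedure) sets one block size: "Randomization will be performed by site in random permuted blocks of 6 by allocation order". The list is held in the eCRF, and its purpose there is: "to define the randomized treatment order (X or Y device) and provide the investigator with this information during the enrolment visit". The allocation ratio is not written, no variation in block size is described, and nothing restricts the sites' knowledge of the size.

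Section 7.1 says: "The randomization procedure will be concealed and assigned off-site". Section 7 describes the design: "This is a prospective international multicenter randomized controlled cross-over open-labeled trial". Section 7.2 adds: "The certified prosthetist (CPO) and physical therapist cannot be blinded".

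Principal investigators work from this protocol. Under section 15.3 they are among those who sign an amendment: "it must be signed and dated by the Sponsor, the Coordinating Investigator and the Principal Investigators".

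On numbers, section 9.1 says: "At least 56 subjects passing screening will be randomized". Nine sites are listed in the Study Overview, and section 7 sets no site quotas: "Patients can be enrolled in a competitive manner without any allocation".

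**The concern.** Off-site assignment hides the list. It does not prevent deduction when the block size is fixed, known, and applied within one site whose staff see every earlier order. The device labels X and Y give no protection once the first patient has been fitted. When one order has been used three times in a block, the rest of that block is determined. Before that point, the less-used order is the better guess.

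Site staff also have some discretion before randomisation. They decide whom to call and when to screen (sections 7.3.1 and 9.1), and they judge whether a candidate shows adequate potential with the trial orthosis (section 9.3.1).

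In this crossover only the order of devices is allocated, so the stake is narrower than in a parallel-group trial. A patient's stable level of balance cancels from the within-patient comparison. What does not cancel is change over the 8 to 9 months of observation, if it differs between the two order groups because of selection. The primary model in section 10.3.2 (Primary efficacy outcome) has one common period effect and a random patient intercept, and neither removes such a difference. Dropout linked to order, and the planned comparison of the groups at enrolment (section 10.3), are exposed in the same way.

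**Working it through.** **Inputs.** Block size 6, by site (section 10.3.2). Nine sites (Study Overview). 56 patients (section 9.1). Relevance limit of 3 Berg points (section 10.4). Assumptions not in the documents: 3:3 blocks, a site that tracks its own orders, and random recruitment at equal rates across sites.

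**The plan's own figure.** The documents give no figure for predictability. The sample size of 56 that enters below does reproduce. The McNemar formula in section 10.1.2, with 1.6449, 0.8416 and a discordant proportion of 0.1333, gives ((1.6449 × 0.3651 + 0.8416 × 0.3399) / 0.1333)² = 44.24. Then 44.24 / 0.8 = 55.3, rounded up to 56.

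**Step 1: one complete block.** All 20 equally likely 3:3 sequences were enumerated.

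| Position in block | 1 | 2 | 3 | 4 | 5 | 6 | Sum |
|---|---|---|---|---|---|---|---|
| Probability the order is certain | 0 | 0 | 0 | 0.10 | 0.40 | 1.00 | 1.5 |
| Probability of a correct best guess | 0.5 | 0.6 | 0.6 | 0.7 | 0.7 | 1.0 | 4.1 |

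The certain share is 1.5 / 6 = 25%, and the share guessed correctly is 4.1 / 6 = 68.3%. Both hold only if every block is filled.

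**Step 2: this trial.** 56 / 9 is about 6 patients per site on average. With competitive recruitment many last blocks stay unfinished, and the certain positions come late in a block. The position probabilities were summed over site totals:

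- 56 patients at random over 9 sites: 16.7% certain (95% range 13% to 20%). 0.167 × 56 is about 9 patients. About 64.5% are guessed correctly.
- Any possible split of 56 patients over at most 9 sites: 11.1% to 24.1% certain.
- If more are randomised: about 18% certain at 70 patients and 22% at 150. Growth is possible, because dropouts are replaced (section 7.3.1) and the interim analysis may increase the sample size (section 10.4).

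**Step 3: possible bias.** Let g be the share of correct guesses and d the difference between steered and other patients in change from period 1 to period 2. The two order groups then differ by (2g − 1) × d in mean change. The device estimate is half the difference between the orders, so

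bias = (2g − 1) × d / 2.

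With g = 0.645, this is 0.29 × d / 2 = 0.145 × d. For an assumed d = 3 it is 0.435 points, and 0.435 / 3 = 14.5% of the plan's relevance limit. If sites acted only on orders that are certain, it would be 0.167 × 3 / 2 = 0.25 points. The value of d is an assumption, and the bias scales in proportion to it.

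**Step 4: varied block sizes within site.** Blocks of 4, 6 and 8 were simulated with an observer who knows the set of sizes. The certain share falls to about 1% to 2.5%. Correct guesses stay at about 65%, because a known tally within a small site still favours the less-used order.

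**The case against.** The case against acting has several parts.

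- **Little motive to steer.** Every patient receives both devices. The C-Brace may be kept for up to 24 months while reimbursement is sought, whichever device came first (section 7.3.10). This stands, and it lowers the likelihood of steering.
- **Limited room for differing trends.** Unstable neurological disease is excluded, and compliant orthosis use over the previous 3 months is required (section 9.3). This also stands in part. It makes a large d less plausible but does not rule one out over 8 to 9 months.
- **The bias figure is extreme.** It needs every site to tally, a suitable patient to be available at each allocation, and all sites to steer the same way. This is correct: 0.145 × d is a worst case. The minimal detectable change of 3.3 to 6.3 points in section 8.2.1 is a measurement threshold in elderly adults, so it gives no basis for a larger d.
- **Late in the trial.** The Study Overview plans the last patient in on 31 December 2021, so few allocations may remain. This affects which remedy applies, not whether the weakness exists.

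Some stronger readings are tempting, and the documents do not support them. A reader might infer that a quarter of all orders are known in advance, but that holds only for completed blocks and is above the maximum of 24.1% possible with 56 patients. A reader might infer that concealment fails altogether. Assignment is off-site, and about 83% of orders are not certain beforehand. A reader might also infer that a first-period comparison is biased, but the plan contains none. Finally, a reader might conclude that one central list is needed because site differences cancel within patients. That is true only of stable site effects. Section 7.3.12 allows restart dates after lockdown to differ by site, which is a reason to keep order balanced within site.

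**Conclusion.** The point holds in a limited form. A fixed block of 6 within each site, disclosed to sites that see every allocation, weakens the concealment stated in section 7.1. About one order in six (about 9 of 56) is certain in advance, at most about a quarter when blocks are completed, and about 64.5% can be guessed. These figures rest on 3:3 blocks, a site that keeps a tally, and random recruitment over 9 sites.

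The effect on the primary result is bounded by the crossover. It requires steered patients to differ in change between periods or in dropout. The worst-case shift is about 0.145 × d, or about 0.4 Berg points at an assumed d = 3. Nothing in the documents shows that steering occurred, and the predictability figures should not be read as evidence that it did. The change is worth making because it is standard and cheap, not because the primary comparison is in evident danger.

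**What to change.** For patients still to be randomised:

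1. Keep randomisation by site, and replace the fixed block of 6 with randomly varying block sizes (for example 4, 6 and 8) in the existing electronic list.
2. Remove the block sizes from section 10.3.2 of the site-facing protocol and record them in a restricted sponsor document.

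This removes nearly all certain predictions (from about 17% to about 1% to 2.5%). It does not remove guessing that is better than chance, which stays at about 65%. A single central list is optional. It would reduce guessing further, but it gives up balance of order within site.

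The cost is a new list and a short amendment, with the signatures and ethics approvals that sections 15.3 and 17.1 require, and slightly less exact balance of order within a site.

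If recruitment is already complete, no change to the list is possible. The report should then state the fixed, disclosed block size as a limitation of concealment.

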10.4 Interim analysis

An interim analysis will be performed after at least 35 patients have completed the study. After the interim analysis, it will be decided whether: 1) the sample size must be increased 2) the study will be

ottobock.	CLINICAL INVESTIGATION PLAN	Document number:	PD-PS00120016A-001
		Version number:	7
Project name	Clinical trial comparing C-Brace to KAFO/SCO	Project no.	PS00120016A

stopped early for futility, or 3) interim hypothesis testing will be done for the primary objective and select secondary objectives.

The interim analysis will be performed for the primary endpoint (BBS). A statistical power calculation will be performed based on the observed intraindividual changes (IIC) between C-Brace and KAFO arms. The following rules will be applied:

1. If the power based on observed mean and standard deviation for the BBS IIC for the intended target of 56 subjects is less than 0.9, the proposed sample size for the study may be increased.
2. If the observed mean IIC is less than 3, the study may be stopped for futility, since this difference is of no clinical relevance.
3. If the power based on observed mean and standard deviation for the BBS IIC with the interim analysis cohort of at least 35 subjects is greater than 0.95, hypothesis testing will be performed at the $\alpha = 0.02$ level to determine statistical significance. In this case, the primary objective will be analyzed at the 0.03 level for the final analysis of the full study cohort at the completion of the study to maintain an overall Type I error rate of 5%. If the power is less than 0.95, hypothesis testing will only be performed at the conclusion of the study and statistical significance determined using $\alpha = 0.05$.

Conditional hypothesis testing may be performed for select secondary objectives using the same method described in rule 3 above.

ottobock.	CLINICAL INVESTIGATION PLAN	Document number:	PD-PS00120016A-001
		Version number:	7
Project name	Clinical trial comparing C-Brace to KAFO/SCO	Project no.	PS00120016A

11 Risk and benefit of the investigation device and clinical investigation

C-Brace is a CE-marked class I medical device. Risk analysis has been conducted and identified risks such as blocking of flexion in knee joints when descending stairs or ramps, unintentional locking during sitting, flexion resistance is not reduced when walking on level ground (swing phase), insufficient extension of knee joint in the stance phase, insufficient extension of the orthosis during standing up. All those identified risk could lead to a fall. After implementation of appropriate measures, the risk analysis concluded that the remaining risks are either acceptable or ALARP (as low as reasonably practicable).

In this clinical study, patients will be randomly assigned to two treatment groups. Treatment group 1 will start with 3 months usage of the patients' KAFO or SCO. The patients will then move to a 3-month period of C-Brace use. Treatment group 2 will start with 3 months of C-Brace use and will then enter into a 4-week washout period before moving to a 3-month period of KAFO/SCO use. This randomization will not add any additional risks to the patients since both groups will use both devices for the same period.

Patients enrolled in the study will enter with their current orthosis (KAFO/SCO). Before performing the clinical tests, patients will receive up to 10h of accommodation training and will be benchmarked according to their ability to use their orthosis. When entering the C-Brace group, patients will again receive up to 10h of accommodation support and an assessment. Patients enrolled in the study who will start with C-Brace, will receive accommodation support and assessment. When switching back to their regular orthosis (KAFO/SCO) they will again receive accommodation and assessment. Therefore, the risks due to switching of the devices in the clinical study are mitigated.

The expected benefit of C-Brace to the patients participating in this study will be comparable to the ones published on C-Brace. The literature published on C-Brace suggests that microprocessor controlled SSCOs offer benefits during walking on level ground, stairs and ramps when compared to conventional KAFOs such as locked KAFOs and SCOs. Biomechanical analysis showed that more physiological swing and stance phase during level walking is possible with C-Brace (Schmalz 2016). Walking on ramps and stairs was also more physiological allowing step-over-step descent. The load on the contralateral limb was reduced. C-Brace also resulted in improved safety and reduction in difficulty of performing activities of daily living (Pröbsting 2016). Subjects report of 91% of the ADLs being safer and 76% of the ADLs less difficult to perform with C-Brace in comparison to their previous orthosis. Greatest functional gain was achieved in the categories Family and Social Life and Sports and Leisure activities. Significant improvements were achieved in the domains of ambulation, paretic limb health, well-being and disturbing sounds of the orthosis.

ottobock.	CLINICAL INVESTIGATION PLAN	Document number:	PD-PS00120016A-001
		Version number:	7
Project name	Clinical trial comparing C-Brace to KAFO/SCO	Project no.	PS00120016A

The new version of C-Brace is smaller and reduced in weight. Furthermore, due to an improved sensor system in the joint unit, sensor at the ankle become obsolete and therefore the design of the orthotic shells can be better adapted to the individual anatomy. Therefore, the benefits of the new C-Brace should be better or at least in the range of those reported for the original C-Brace. The sensor technology that does not require an ankle sensor is already applied in the C-Leg 4. First clinical results showed high satisfaction (94% of users reported to be either satisfied or very satisfied) and 72% of users reported better or much better swing initiation compared to their previous prosthesis (Kraft 2015, Wismer 2016).

Therefore, it can be concluded that the risks associated with the use of the device are acceptable when weights against the benefits that this research can generate in terms of further development of C-Brace to the subjects and patient population in general.

Risk-benefit assessment of the clinical investigation during the COVID-19 pandemic situation

In this clinical study, patients are asked to visit the study site for 6 visits, as well as for additional visits if required by the site for the purpose of fitting of assistive devices (KAFO/SCO or C-Brace). In most likely all cases, patients will have to travel to get to the respective study site.

All patient appointments will be done in accordance with the effective national, state and local regulations on contact and /or travel restrictions due to the COVID-19 pandemic. Whenever possible, the number of appointments at the study site will be reduced and patient assessments will be managed over the phone (unless the patient needs assistance with their medical device).

Prior to arriving to the first visit since the start of the COVID-19 pandemic, a risk factors assessment shall be conducted in accordance with the procedures valid in the sites in order to decide whether the patient should attend the next visit at the site (i.e. to continue in the study for patients already enrolled or to attend an enrollment visit for patients interested in participating in the study).

During patient visits, every effort will be taken to minimize a potential infection risk by:

- limiting the number of staff to a minimum,
- providing sufficient protection material to the patients as well as to the staff (gloves, coats, face masks, hand hygiene practices, cleaning of assistive devices and surfaces, and other precautions that will be taken before and after every patient visit),
- minimizing the length of stay necessary for the patients and
- maximizing the distance between patients and staff as much as possible.

ottobock.	CLINICAL INVESTIGATION PLAN	Document number:	PD-PS00120016A- 001
		Version number:	7
Project name	Clinical trial comparing C-Brace to KAFO/SCO	Project no.	PS00120016A

In case of increasing health risk or for any other reason, all enrolled subjects may withdraw from the study at any time.

Therefore, it can be concluded that, given that all mitigation measures described above are taken, the risks associated with a study visit during the COVID-19 pandemic are acceptable when weighed against the benefits that this research can generate for the individual and the population in general.

If the study is still running after the COVID-19 pandemic situation, some of the precautions will not be necessary anymore. In this case, potential subjects will be invited to attend an information meeting with the Principal Investigator (PI). If the subject is considered by the PI to be eligible for participation in the study, he/she will be fully informed about the study and given sufficient time to consider and given an opportunity to ask questions or to discuss participation with his/her general practitioner or therapist. Subjects who wish to enter the trial will then sign the consent form and subsequently be enrolled.

ottobock.	CLINICAL INVESTIGATION PLAN	Document number:	PD-PS00120016A-001
		Version number:	7
Project name	Clinical trial comparing C-Brace to KAFO/SCO	Project no.	PS00120016A

12 Management of adverse events

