Objective	To evaluate effectiveness and benefits in patients with lower limb impairment in activities of daily living comparing the C-Brace microprocessor – controlled stance and swing orthosis to standard of care use of knee ankle foot orthosis/stance control orthoses
Design	Prospective international multicenter open-labeled randomized controlled cross-over trial
Devices	C-Brace, KAFOs, SCOs
Primary Efficacy End-point	Improvement of static and dynamic balance by using C-Brace compared to KAFO /SCO
Secondary Endpoints	
 1. To evaluate the effect of the C-Brace compared to KAFO/SCO on gait, balance, plain level walking, walking during more challenging tasks and divided attention tasks during walking. 2. To assess and compare the safe use of the C-Brace compared to KAFO/SCO in regards to falls: frequency of falls, severity of falls, fall-related injuries, fear of falling and related treatment efforts. 3. Evaluation of patient`s confidence in performing various ambulatory activities without falling using C-Brace compared to KAFO/SCO. 4. Assessment of quality of life and re-integration to normal living using C-Brace compared to KAFO/SCO. 5. Assessment of disability and impact on productivity. 6. Assessment of patient`s C-Brace satisfaction and usage habits compared to KAFO/SCO 7. Reduced probability of falling more than once by using C-Brace compared to KAFO / SCO

ottobock.	CLINICAL INVESTIGATION PLAN	Document number:	PD-PS00120016A-001
		Version number:	7
Project name	Clinical trial comparing C-Brace to KAFO/SCO	Project no.	PS00120016A

Clinical Follow-up	Screening, 2 baselines, visit 1 after 3 months usage of device 1 at home, visit 2 after 3 months usage of device 2 at home
No of patients	At least 56 randomized

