7.3 Study visits and procedures

7.3.1 Patient enrollment

This study will enroll up to 150 eligible patients. At least 56 subjects passing screening will be randomized. Dropouts shall be replaced, a dropout rate of 20% is assumed. Recruitment planning shall be done in accordance with the capabilities of the centers. Competitive recruitment shall be allowed. All means to increase recruitment shall be taken.

ottobock.	CLINICAL INVESTIGATION PLAN	Document number:	PD-PS00120016A-001
		Version number:	7
Project name	Clinical trial comparing C-Brace to KAFO/SCO	Project no.	PS00120016A

Treatment failures: C-Brace must be fitted according to Ottobock instructions. During study visits, the C-Brace fitting quality will be checked; poor fitting quality needs to be corrected and may be reported as adverse event (AE) or adverse device effect (ADE). For definitions, please refer to section 12.2.

Patients who do not comply with using the C-Brace at least 1-2 hours per day 5 days per week will be included in the intention to treat analysis only; however, they will be excluded from the per-protocol analysis.

Potential patients will be called by the participating sites and pre-screened for study eligibility. In addition, patients contacting the sites or visiting them on a routine basis can be also pre-screened.

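### Rule 1 of the interim analysis allows N to be raised on the observed device difference, then tested at an unadjusted 0.05, so the stated 5% type I error is not guaranteed on that path

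*Combined protocol and SAP*

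**What the plan says.** Section 10.4 places the interim after at least 35 completers and bases it on the intraindividual BBS change (IIC) between devices.

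- Rule 1: when "power based on observed mean and standard deviation for the BBS IIC for the intended target of 56 subjects is less than 0.9", then "the proposed sample size for the study may be increased".
- Rule 2: "If the observed mean IIC is less than 3, the study may be stopped for futility".
- Rule 3: if power at the interim size exceeds 0.95, the primary hypothesis is tested at 0.02 and later at 0.03, "to maintain an overall Type I error rate of 5" percent. Otherwise, "hypothesis testing will only be performed at the conclusion of the study and statistical significance determined using" 0.05.

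No formula, target power or maximum is attached to the increase in rule 1. The only ceiling is general: "This study will enroll up to 150 eligible patients" (section 7.3.1) and "Up to 150 patients fulfilling the inclusion and exclusion criteria will be enrolled in the study" (section 9.1). The Study Overview gives the randomised number as "At least 56 randomized". The confirmatory mixed model in section 10.3.2 (Primary efficacy outcome) has no stage weights or other adjustment for a changed N.

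**The concern.** Rule 1 uses the observed mean as well as the SD, so the decision to enlarge depends on the interim treatment effect. When N depends on that effect and the data are pooled into an ordinary test, the nominal level is no longer assured. Enlarging after a weak interim raises the chance of a false positive; enlarging after a promising one lowers it. The net effect depends on the policy followed, and the plan does not state one.

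The plan sets itself a 5% overall target, but its only protection is the 0.02/0.03 split in rule 3. If that split never applies to an enlarged trial, error control there rests on choices made after the device comparison is known. Rule 2 does not settle the matter, because it says only that the study *may* stop and no order of precedence is given.

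**Working it through.** **The plan's 56.** Section 10.1.2 uses p_diff = p_disc = 0.1333, one-sided 0.05 and power 0.8:

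n = [(1.645·√0.1333 + 0.842·√(0.1333 − 0.1333²)) / 0.1333]² = 44.24; 44.24/0.8 = 55.3, rounded up to 56.

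This reproduces. The 56 is therefore a randomised number already inflated for 20% dropout. The IIC exists only for paired data: 56 × 0.8 ≈ 45 pairs. Power of 0.90 at 56 pairs is 0.83 at 45.

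**Can rules 1 and 3 both fire?** Power is 1 − F(t_crit; n−1, δ√n), with F the noncentral t distribution, δ = mean/SD and alpha 0.05.

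- Rule 1 (n = 56, power below 0.9): δ below 0.396 one-sided, 0.441 two-sided.
- Rule 3 (n = 35, power above 0.95): δ above 0.568 one-sided, 0.627 two-sided.

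The regions do not overlap, so every enlarged trial ends at a plain 0.05. Both versions are given because section 10.4 states no sidedness, and section 10.1.1 names a one-tailed test although its 6.4557 is the two-sided result (one-sided: 5.03).

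**When rule 1 fires.** At the planning SD of 4.9085 it needs an observed mean below 0.396 × 4.9085 = 1.94, inside the rule 2 region (below 3). It reaches outside that region only if the SD exceeds 3/0.396 = 7.6. At the planning values (6.6429, SD 4.9085; noncentrality 1.353 × √35 = 8.01; limit 0.396 × √35 = 2.34; 34 df) the probability is about 2.5e-8. It is 0.06 at mean 6.64 and SD 10, 0.11 at mean 3 and SD 4.9085, and 0.54 at mean 3 and SD 8.

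**Why the policy matters.** Under H0, given interim z1 at n1 = 35, the pooled test rejects with probability P(Z > (1.645·√(n1+n2) − √n1·z1)/√n2). At z1 = 0, going from 56 to 112 pairs moves the cut-off from 2.69 to 1.98, so this probability rises from 0.004 to 0.024. At z1 = 2 the cut-off moves from 0.10 to 0.64, and the probability falls from 0.46 to 0.26.

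**Type I error.** Simulation with 1,000,000 null trials per setting, one-sided, rule 3 path included, rule 2 not applied except in the last paragraph. N is raised toward 90% power at the observed mean and SD. Policies and caps are assumptions, because the plan gives none.

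| Policy | Starting pairs | Cap 70 | Cap 112 | Cap 150 |
|---|---|---|---|---|
| Raise only if observed difference is positive | 56 | 0.051 | 0.053 | 0.053 |
| | 45 | 0.053 | 0.054 | 0.054 |
| Also go to the cap if zero or negative | 56 | 0.052 | 0.057 | 0.059 |
| | 45 | 0.053 | 0.058 | 0.061 |
| Raise only if 90% power is reachable within the cap | 56 | 0.050 | 0.047 | 0.044 |
| | 45 | 0.047 | 0.041 | 0.038 |

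A separate numerical integration gives 5.2% and 5.3% for the first policy from 56 pairs (caps 112 and 150) and 5.6% and 5.9% for the second. If 0.05 is two-sided, the upper tail of 0.025 becomes 0.028 and 0.030 at cap 150.

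With rule 2 always enforced, the one-sided error is 0.001 at the planning SD, 0.024 at SD 12 and 0.030 at SD 15.

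**The case against.** The strongest reply is that the excess needs conduct the plan points away from. At the planning SD, rule 1 fires only where rule 2 already calls the difference clinically irrelevant, and section 10.4 lists enlarging, stopping and interim testing as alternatives. This stands as a limit on the size of the problem. It does not remove it: at observed means below 1.94 the text permits both stopping and enlarging, and does not say which prevails.

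A second reply is that the enrolment ceiling already bounds N. It does, so a reader who infers that the trial could grow without limit goes too far. But rule 1 does not refer to the ceiling, and the ceiling may include screening failures: section 7.3.2.4 counts a failed DTO test as one, while section 9.1 speaks of patients who fulfil the criteria. At 20% dropout, 150 randomised give 150 × 0.8 = 120 pairs, so the cap-150 column is not reachable on the plan's own assumption.

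A reader might also take 6% or more as the trial's error rate. The 0.057 to 0.061 figures require enlarging to the cap when the observed difference is zero or negative, where no N gives 90% power. Choosing the most unfavourable N at every interim result would give 6.3% at cap 112 and 6.7% at cap 150 from 56 pairs, but nothing in the plan prescribes that.

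**Conclusion.** The point holds as a gap in error control. Rule 1 permits an effect-dependent increase with no new-N rule and no maximum of its own, and every enlarged trial is tested at an unadjusted 0.05. The stated 5% is then not guaranteed.

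If rule 2 is left unused, the one-sided excess is 0.1 to 0.4 percentage points when N rises only on positive differences. It is up to about 0.9 points at cap 150 from 56 pairs (1.1 from 45) when N is raised regardless of sign. Enforcing rule 2 removes the excess. These sizes rest on assumed policies and caps and an interim at exactly 35 pairs.

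The documents do not support the inference that the trial as planned has an inflated error rate, or that an increase is likely. The trigger becomes realistic only if the effect is much smaller or the SD much larger than planned; those planning values come from 14 patients. The change should be made, but it is not urgent beyond being settled before the interim.

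**What to change.** Replace rule 1 with wording such as:

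> Power in rule 1 is computed for the number of patients expected to provide paired BBS data when 56 are randomised, with the alpha and sidedness of the final test. If it is below 0.9, that number is raised to the smallest value giving power 0.9 at the observed mean and SD, and only if that value does not exceed a stated maximum (for example 112 pairs, within the enrolment ceiling). Otherwise N is not increased.

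The unadjusted 0.05 test can then stay (last policy in the table). At 20% dropout, 112 pairs means 112/0.8 = 140 randomised, which leaves only 10 places under the 150 if screening failures count toward it.

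The cost is wording only. The downside is that N is not increased, and no power gained, when the observed effect is too small. At a true difference of 3 with a maximum of 112, from 56 pairs, one-sided power is 0.88 at SD 8 and 0.73 at SD 10. With no increase at all it is 0.870 and 0.716. Resizing at a fixed difference of 3 without adjustment gives 0.91 and 0.89, but its error is 0.052 to 0.053 at SD 8. Repeating the simulation of the proposed rule from 45 pairs (400,000 trials) gives about 0.82 and 0.66.

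If the sponsor wants increases outside that zone, an inverse-normal combination test holds 5% for any new N. Its weights must be fixed before any between-device comparison. The data cut must also keep the interim number n1 clearly below the planned number of pairs n, because the second-stage weight √(1 − n1/n) vanishes as n1 reaches n. From 45 pairs, with N resized at a difference of 3, its power is 0.885 against 0.902 for the unadjusted test at SD 8, and 0.834 against 0.887 at SD 10.
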